Consenting process. If the patient passed the screening, the research coordinator will then conduct a recruitment home visit to the eligible patient within five business days. During the visit, the coordinator will provide the patient with a detailed description of the research study and go over the informed consent process. If the patient does not provide consent during the recurrent home visit but decides to participate in the study afterwards, a study outcome assessor will obtain consent at the beginning of the baseline assessment visit. If the patient decided not to enroll, the reason(s) of rejection will be recorded.

Baseline assessment. The enrolled patient will be then referred to the study outcome assessor, who will schedule the patient to obtain the consent, if not yet obtained by the research coordinator, and complete the baseline assessments at the participant's home. The baseline assessment should occur within seven business days of the recruitment visit. The assessor will be blinded to patient group assignments. The blinded outcome assessor will conduct the following assessments during the baseline evaluation visit. These assessments are listed in suggested order. The outcome evaluator will alternate between self-reported assessments and performance-based assessments as well as upper extremity performance tests and lower extremity performance tests to reduce the testing burden for patients. Additionally, short breaks (one to five minutes) between assessments will be provided to patients as needed.

1. Demographic information of age, gender, race/ethnicity, chronic conditions, and number of medications
2. Assessment of Motor and Process Skills
3. Activity Measure of Post-Acute Care Home Health Short Form
4. Jebsen Hand Function Test
5. Box and Block Test
6. PEG three-item scale
7. Patient Health Questionnaire-9
8. Timed-Up-and Go
9. Short Physical Performance Battery
10. Saint Louis University Mental Status Exam.

The research coordinator will extract the patient's OASIS self-care item scores (scores at the start of care and discharge) from medical chart when the patient has been discharged from home health care or 60 days after admission.

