Randomization. Randomization will occur after the baseline assessment. [name] (Co-I) will generate a randomization list using a computer software and seal the list in opaque envelopes. The on-site research coordinator will open one envelope after a patient has completed the baseline assessments. If the patient is assigned to the ADL-enhanced group, the coordinator will notify the study OT to start intervention.

Post-intervention evaluation.

The satisfaction survey will be given to the patient in the experimental group after the last visit of ADL-enhanced intervention by the research coordinator over the phone.

For the group that will receive the ADL-enhanced program, the post-intervention evaluation conducted by the blinded outcome assessor will occur within seven business days after the completion of the last visit of usual home health rehabilitation therapy or ADL-enhanced intervention, whichever occurs last. For the control group, the post-intervention evaluation conducted by the blinded outcome assessor will occur either 6 weeks after the baseline assessment or after the last usual home health visit, whichever occurs last. Patients will be instructed not to discuss their therapy content with the blinded outcome assessor and vice versa. The following assessments will be administered during the post-intervention evaluation visit.

1. Assessment of Motor and Process Skills
2. Activity Measure of Post-Acute Care Home Health Short Form
3. Jebsen Hand Function Test
4. Box and Block Test
5. Timed-Up-and Go
6. Short Physical Performance Battery
7. Adverse events questionnaire

The research coordinator will extract the patient's OASIS self-care item scores (scores at the start of care and discharge) from medical chart when the patient has been discharged from home health care or 60 days after admission.

One-month follow-up evaluation.

The one-month follow-up evaluation conducted by the blinded outcome assessor will occur within seven business days one month after the completion of the last visit of usual home health rehabilitation therapy or ADL-enhanced intervention (Day 30 post intervention), whichever occurs the last. Patients will be instructed not to discuss their therapy content with the blinded outcome assessor and vice versa. The following assessments will be administered during the one-month follow-up evaluation visit.

1. Assessment of Motor and Process Skills
2. Activity Measure of Post-Acute Care Home Health Short Form

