3. Jebsen Hand Function Test
4. Box and Block Test
5. Timed-Up-and Go
6. Short Physical Performance Battery
7. Adverse events questionnaire

Final evaluation or three-month follow-up evaluation.

The final evaluation will occur over the phone by the research assistant or coordinator within seven days three months after the completion of the last visit of usual home health rehabilitation therapy or ADL-enhanced intervention (Day 90 post intervention). The following assessments will be administered during the final evaluation.

1. Activity Measure of Post-Acute Care Home Health Short Form
2. Adverse events questionnaire

Data analysis plan.

Preliminary analysis. We will compare participant demographics and covariates (e.g., pain levels) between the two groups. Variables with statistically significant differences will be included in the subsequent statistical models as covariates. We will graph spaghetti plots for repeated measurements and examine for outliers.

Data analysis. Since ADL and physical functioning outcomes will be collected over three time points (baseline, post-treatment, one-month follow-up), the mixed-effects linear regression modeling will be conducted to fit the data, in which a random-effects term is included to accommodate within-subject data correlation and a quadratic growth curve is included to describe the temporal trend of the response.

For **Aim 1**, which will estimate the preliminary effect of the ADL-enhanced program on improving ADL, three separate mixed-effects regression analyses will be conducted for the Motor Skills scores of the Assessment of Motor and Process Skills (the primary outcome), the Activity Measure of Post-Acute Care Home Health Short Form, and the OASIS self-care items, in each of which sex, race, age, and other covariates will be included in the model.

For **Aim 2**, which will estimate the preliminary effect of the ADL-enhanced program on physical functioning of the upper extremity and lower extremity, four similar separate analyses will be conducted for the Box and Block Test, Jebsen Hand Function Test, Timed-Up-and Go, and Short Physical Performance Battery.

For **Aim 3**, the program completion rate and satisfaction rate will be compared to the benchmark, 75%. Fisher's Exact Test will be performed to compare the proportion of patients who experience adverse events of hospitalization, emergency room visits, or falls (adverse event rate) between the two groups.

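### Beyond sex, race and age, covariates are chosen by significance tests of baseline differences, so entry depends on chance imbalance and not on prognostic value

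*Combined protocol and SAP*

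**What the plan says.** In the Data analysis plan, the Preliminary analysis paragraph begins: "We will compare participant demographics and covariates (e.g., pain levels) between the two groups". It continues: "Variables with statistically significant differences will be included in the subsequent statistical models as covariates". No significance level is given.

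The Aim 1 paragraph states that "sex, race, age, and other covariates will be included in the model". The three named variables are therefore fixed; the rest are not listed anywhere. Aim 2 is to be analysed in a similar way, so the rule reaches seven models (three for Aim 1, four for Aim 2).

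The outcome's baseline value is one of the modelled time points and does not depend on the rule. For the time course, "a quadratic growth curve is included to describe the temporal trend of the response", but the treatment contrast is not written out.

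Under Enrollment, baseline, and randomization: "Randomization will occur after the baseline assessment". The candidate variables are in the baseline assessment list. Its first item is "Demographic information of age, gender, race/ethnicity, chronic conditions, and number of medications", and it also contains the PEG pain scale, the PHQ-9 and the SLUMS cognitive exam.

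**The concern.** Allocation comes after the baseline measurements, so if it is carried out as planned, any baseline difference between arms is chance. A significance test of that difference asks a question whose answer is already known. It says nothing about which variables predict the outcome, and prediction is what makes a covariate worth including.

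Two errors follow. A variable unrelated to outcome can enter by luck. A strong predictor with a moderate imbalance is left out, because the test has little power with 24 per arm. The content of the final model is then settled by the draw of the randomization list. At stake are the precision of the effect estimate and, in some trials, a part of a chance imbalance left inside it. Because the contrast is not stated, a reader also cannot tell what a selected covariate would do in the model.

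**Working it through.** The plan gives no alpha, effect size, SD or correlation behind its sample size, so there is no figure of its own to reproduce. **From the documents:** 48 patients, 24 per arm (Study design overview); randomization after baseline; candidates PEG, PHQ-9 and SLUMS, plus chronic conditions and number of medications. **Assumed:** two-sided 0.05 tests, independent candidates, and the effects and correlations named below.

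**Entry threshold.** t(0.975, 46 df) × √(2/24) = 2.013 × 0.289 = 0.581 SD. An imbalance of 0.5 SD gives t = 0.5/0.289 = 1.73, p = 0.090, and the variable is left out.

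**Entry by chance.** Each candidate enters about 5% of the time; simulated entry was 4.8% to 5.1% at covariate-outcome correlations of 0, 0.3, 0.5 and 0.7. At least one enters with probability 1 − 0.95³ = 14.3% for three candidates and 1 − 0.95⁵ = 22.6% for five.

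**Power, the rule versus always including the covariate** (8,000 simulated trials per setting):

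| Analysis | Effect | Setting | Rule | Always in |
|---|---|---|---|---|
| Post-treatment level, no baseline | 0.8 SD | correlation 0.3 | 77.1% | 80.1% |
| | | correlation 0.5 | 77.4% | 87.0% |
| | | correlation 0.7 | 79.9% | 96.4% |
| Baseline as covariate, correlation 0.6 with both visits | 0.7 SD | pre-post 0.5 | 78.0% | 84.6% |
| | | pre-post 0.8 | 97.5% | 97.8% |

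The effects differ between the two analyses, so power should be compared within rows only. With baseline in the model, the empirical SE falls from 0.247 to 0.229 (7%) at pre-post correlation 0.5 and from 0.174 to 0.171 (2%) at 0.8. At covariate correlation 0.4 the gain in SE is 2% or nil.

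**Imbalance left in the estimate.** For an imbalance d and covariate correlation r, the shift is d × r without baseline and d × r × (1 − pre-post correlation) with it. With d = 0.5 (not flagged) and r = 0.6:
- no baseline: 0.5 × 0.6 = 0.30 SD;
- baseline in, pre-post 0.5: 0.30 × 0.5 = 0.15 SD;
- baseline in, pre-post 0.8: 0.30 × 0.2 = 0.06 SD;
- change contrast: 0.6 × 0.5 − 0.6 × 0.5 = 0.

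**Type I error under the rule.** Overall it is 4.7%, 4.5% and 3.7% without baseline (correlation 0.3, 0.5, 0.7) and 4.8% to 5.0% with baseline (correlation 0.6). In trials with an unflagged imbalance above 0.4 SD, it is about 10-12% without baseline (correlation 0.5 to 0.7) and 6-8% with baseline (correlation 0.6). Such trials are about 12% of the total per covariate: 0.4/0.289 = 1.39, two-sided tail about 0.17, less the 0.05 that are flagged.

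**Group-by-time contrast.** In a random-intercept model with three visits and quadratic time by group (60 simulated datasets), adding a main-effect covariate changed the group-by-time estimate by less than 10⁻¹³ with complete data. With 15% of follow-up visits missing, the SE was 0.273 without the covariate and 0.272 with it. The SE of the group main effect did fall, from 0.243 to 0.178 (correlations 0.6).

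**The case against.** The strongest objection is that the rule may do no harm under the most natural reading. The hypotheses speak of larger improvement and smaller decline, and baseline is modelled alongside the later visits. That points to a group-by-time contrast, in which a main-effect covariate does nothing, whether selected by a test or prespecified. This stands, and it is why a covariate list alone would not be a sufficient repair. It does not rescue the rule: under this reading the adjustment step cannot do its job, and under the others it loses precision.

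Second, the largest power gaps come from an analysis without baseline, which is not what the plan describes. This also stands. Once baseline is used, the gain is appreciable only for a strong covariate and a modest pre-post correlation. Nothing in the documents shows that PEG or SLUMS reaches a correlation of 0.6. The simulated analyses also omit sex, race and age, and overlap with those would shrink the gain further.

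Third, overall type I error is not inflated. Agreed; the higher figures apply only to the trials described above.

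Fourth, the plan never says outright that the unlisted covariates are only those that pass the test. Pain is called a covariate before any testing, and PEG, PHQ-9 and SLUMS are scheduled at baseline only, as intended covariates would be. That is a fair reading, but no list and no other rule appears. If there is an intended list, it needs to be written down, and the test would still add variables to it by chance.

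Last, this is a pilot. Its primary objective is nevertheless to estimate an effect, and with 48 patients chance imbalances are large and precision is scarce.

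**Conclusion.** The concern holds. The only stated rule for adding covariates beyond sex, race and age selects on chance imbalance, and there is no reading of the model under which it does what it is meant to do.

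The size depends on the contrast. For a post-treatment level or group main effect, the loss of power in these settings runs from negligible to about 7 percentage points with baseline adjusted for, and from 3 to about 16 points without it. For a group-by-time contrast it is nil with complete data. Reported standard errors are not too small on average.

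All of these figures rest on an assumed two-sided 0.05 level, assumed effects of 0.7 or 0.8 SD and assumed correlations. The entry threshold rests only on the 0.05 level and 24 per arm. The chance-entry probabilities also need independent candidates. The point does not invalidate the trial, but it should be corrected.

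**What to change.** - Delete the sentence that selects covariates by significance test.
- Before unblinding, fix a short covariate list to be used whatever imbalance is seen: sex, race, age, and one or two variables already collected and expected to predict outcome (for example PEG and SLUMS). Keep the additions to one or two, because a weak covariate adds nothing once baseline is in the model.
- Write out the treatment contrast, for example the between-arm difference at post-treatment.
- Let the baseline outcome and the covariates act on the post-baseline values, either in ANCOVA form or through covariate-by-visit terms. Without this step the list would have no effect on a group-by-time contrast.
- Report the baseline table descriptively, without p-values.

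The cost is a modest respecification of the model, more than a one-sentence edit, and a few degrees of freedom out of 48 patients; covariate-by-visit terms use more than the ANCOVA form. No new data and no extra patient burden are involved.

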Project Title

Synergizing home health rehabilitation therapy to optimize patients' activities of daily living

Investigators

PI: [name], OTR/L, FGSA, UF Department of Occupational Therapy

CO-I: [name], PT, UF Department of Physical Therapy

CO-I: [name], UF Department of Biostatistics

Conflict of interest

All the investigators declare no conflict of interest.

Clinical Trial Registration #: NCT05411393

UF IRB202102816

Supported by the National Institute on Aging (R21 AG076972)

Date: 1/30/2024

Abstract

Regaining the ability to take care of oneself after an illness or medical episode is critical for older adults to maintain independent living at home in the community. Each year, 3 to 4.5 million older adults receive home health care services that provide skilled rehabilitation therapy in their home. These patients experience reduced capacity to perform activities of daily living (ADL) independently, which is a significant risk factor for long-term care placement. Recent data has shown that nearly 40% of home health patients do not improve in ADL at discharge. There is currently a lack of evidence-based rehabilitation programs in home health. Increasing activity-based intervention in home health care rehabilitation could be the key to improve patients' ADL independence. The objective of this study is to pilot test an ADL-enhanced program as an adjuvant therapy to usual home health rehabilitation to improve patients' ADL outcome. The ADL-enhanced program facilitates patients' participation in ADL first by lowering the task demand using a compensatory approach. As the patient increases physical capacity, the ADL-enhanced program shifts to a restorative approach, which increases the task demand to help the patient channel the improved physical capacity to better activity performance. Our specific aims were to: 1) estimate the preliminary effect of the ADL-enhanced program on improving ADL; 2) estimate the preliminary effect of the ADL-enhanced program on improving physical functioning of the upper extremity and the lower extremity; and 3) assess the program completion rate, satisfaction rate, and adverse event rate (e.g., falls and hospital admissions).

Study Objectives

Primary Objective.

The primary objective is to estimate the preliminary effect of the activities of daily living (ADL)-enhanced program on improving ADL at treatment completion, one month, and 3 months after the completion.

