Hypothesis: Patients who receive the ADL-enhanced program plus usual rehabilitation therapy will show greater improvements in the Motor Skills scores of the Assessment of Motor and Process Skills (the primary outcome), Self-care items in the Outcome and Assessment Information Set (clinical outcome), and Activity Measure for Post-Acute Care Home Health Short Form (patient-reported outcome) at treatment completion and less decline at 1-month and 3-month follow-up than usual rehabilitation therapy.

Secondary Objectives.

Secondary objective 1: To estimate the preliminary effect of the ADL-enhanced program on improving physical functioning at treatment completion and one month after the completion.

Hypothesis 1: Patients who receive the ADL-enhanced program plus usual rehabilitation therapy will show greater improvements in the Box and Block Test (upper extremity physical function), Jebsen Hand Function Test (upper extremity physical function), Timed-Up-and-Go Test (lower extremity physical function), and Short Physical Performance Battery (lower extremity physical function) at treatment completion and less decline at one-month follow-up than usual rehabilitation therapy.

Secondary objective 2: To assess the completion, satisfaction, and adverse event rates of the ADL-enhanced program.

Hypothesis 2a: We hypothesize that the program completion and satisfaction rates will be greater than 75%.

Hypothesis 2b: Fewer patients who receive the ADL-enhanced program will have hospitalizations, emergency room visits, and falls than patients who receive usual rehabilitation therapy at 1-month and 3-month follow-up.

Background and Rationale

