Restorative approach procedures. The study OT will deliver the restorative approach starting at the 3rd visit. The selected self-care tasks include any in-home activities that the patient does to take care of self and others, which are not limited to basic ADL. In the beginning of each visit, the study OT and the patient together identify 2 or 3 activities where the patient has experienced limitations or difficulties. The study OT will apply one or two activity grading principles to each selected activity. The intervention intensity will be kept at the moderate level (somewhat hard) using the Omni Scale, which is a rated perceived exertion scale. For example, if a patient experiences difficulty to returning pantry items to overhead shelves, the study OT can let the patient wear a weighted wrist cuff while sorting pantry items (increase the load), restore items to an overhead versus shoulder-high shelf (increase the movement distance), restore items into different locations on the shelves (change of movement direction), speed up while storing items (increase the movement speed), store 10 pantry items versus store five items at a time (increase the endurance), or carry groceries with a shopping bag and store pantry items from the groceries to the overhead shelves (increase the activity complexity by combining two tasks, carrying groceries and sorting the pantry items after shopping). Patients will practice each selected task for 15 to 20 minutes with a rest break if needed.

Allowed interventions. All participants will receive the care plan approved by their home health agency. The care plan should include regular home health rehabilitation therapy.

Adherence Assessment. The adherence for the ADL-enhance intervention will be evaluated by the number of sessions that the patient is able to complete within the study period (60 days).

Study Procedures.

[figure not shown]
6.1. Schedule of Evaluations.

	Baseline	Post-intervention (Post intervention \pm 7 Business days) ⁺	One-month follow-up (Day 30 post intervention \pm 7 Business days)	3-month follow-up (Day 90 post intervention \pm 7 Business days)
Assessment of Motor and Process Skills	x	x	x	
Activity Measure for Post-Acute Care Home Health Short Form	x	x	x	x
OASIS self-care items from chart review	x	x		
Box and Block Test	x	x	x	
Jebesen Hand Function Test	x	x	x	
Timed-Up-and-Go Test	x	x	x	
Short Physical Performance Battery	x	x	x	
PEG three-item scale	x			
Patient Health Questionnaire-9	x			

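### The analysis plan assumes three time points for every outcome, but AM-PAC has four and OASIS two: the 3-month part of the primary objective has no stated analysis, and the OASIS quadratic is not identified on visit time

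*Combined protocol and SAP*

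**What the plan says.** Under Data analysis plan, the Data analysis paragraph gives the reason for the model: "Since ADL and physical functioning outcomes will be collected over three time points (baseline, post-treatment, one-month follow-up"). On that basis it chooses a mixed-effects linear regression in which "a quadratic growth curve is included to describe the temporal trend of the response". For Aim 1, "three separate mixed-effects regression analyses will be conducted for the Motor Skills scores" of AMPS, for AM-PAC and for the OASIS self-care items. Aim 2 uses the same approach for four physical tests. The arm-by-time terms and the coding of time (visit number or days) are not written out.

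The Primary Objective concerns "improving ADL at treatment completion, one month, and 3 months after the completion". Its hypothesis names AMPS Motor, OASIS and AM-PAC together and predicts greater improvement "at treatment completion and less decline at 1-month and 3-month follow-up than usual rehabilitation therapy".

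The Schedule of Evaluations has four columns, the last headed "3-month follow-up (Day 90 post intervention". In it, AM-PAC is marked in all four columns, AMPS in the first three and OASIS in the first two. The section on the three-month evaluation agrees: "The final evaluation will occur over the phone by the research assistant or coordinator", and its list contains AM-PAC and the adverse events questionnaire only. The baseline and post-intervention sections confirm that OASIS supplies two scores per patient, at start of care and at discharge.

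**The concern.** The premise of three occasions is right for AMPS and the four physical tests, but wrong for two of the three Aim 1 outcomes.

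For AM-PAC it leaves out the only ADL measurement at 3 months. Followed as written, the plan gives no estimate for that part of the primary objective. Whether the fourth visit enters the model, and which contrast is reported, could then be decided after the data are seen.

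For OASIS it asks for a curve through two points. Depending on how time is coded, software would drop a term, fail to fit, or estimate curvature purely from differences between patients in length of care.

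There is also a lesser wording problem. Read outcome by outcome, the hypothesis covers AMPS at 3 months and OASIS at 1 and 3 months, which are not measured. That is 3 of the 9 combinations (3 outcomes × 3 occasions).

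**Working it through.** **Inputs from the documents.** 24 patients per arm (Study design overview); occasions per outcome (Schedule of Evaluations and visit lists); follow-ups 30 and 90 days after completion; a six-week term, 42 days, in the schedule footnote.

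**Assumptions.** Arm-specific linear and quadratic terms. Completion at day T = 42, with 60 and 70 as alternatives. Complete data and compound symmetry, with correlation ρ = 0.6 where a value is needed.

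**1. The plan's count of three.** It is reproduced for 5 of 7 outcomes: AMPS, Box and Block, Jebsen, Timed-Up-and-Go and SPPB. It fails for AM-PAC (4) and OASIS (2).

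**2. Is the quadratic identified?** The fixed-effects design is [1, t, t², arm, arm·t, arm·t²], 6 parameters, with visit as time.

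| Outcome | Visits | Cell means (2 arms) | Rank |
|---|---|---|---|
| AMPS, physical tests | 3 | 6 | 6 of 6 (saturated) |
| AM-PAC, all visits | 4 | 8 | 6 of 6 |
| OASIS | 2 | 4 | 4 of 6 |

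With curvature shared between arms, OASIS has rank 4 of 5. Coding its two visits as days 0 and 42 gives the same ranks. Adding the difference-in-change contrast as a row leaves the rank at 4, so that contrast is estimable. Adding the arm·t or the arm·t² coefficient alone raises it to 5, so neither is identified.

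**3. OASIS on actual dates.** If intervals vary between patients the design can reach full rank, but each patient still has two scores, so curvature comes only from between-patient timing. With assumed intervals of mean 42 days and SD 3, 7 or 12 (limited to 14–60 days) and ρ = 0.6, the SE of the arm·t² term, scaled to day 42, is about 13, 6 or 4 times that of the simple difference in change. The difference in change at day 42 costs little: its SE is 1.02 to 1.10 times as large.

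**4. Can the three-visit AM-PAC curve supply month 3?** The extrapolation weights w are [1, t₃, t₃²] times the inverse of the three-visit design, with t₃ = T + 90. On the change scale, subtract 1 from the baseline weight. Under compound symmetry the SE ratio to the observed month-3 change is √(sum of squared weights / 2), whatever ρ is.

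- T = 42: w = 1.79, −6.29, 5.50. Change weights 0.79, −6.29, 5.50 have sum of squares 70.4; √(70.4/2) = 5.9.
- T = 60: w = 1.00, −5.00, 5.00. Sum of squares 50; √(50/2) = 5.0.
- T = 70: w = 0.77, −4.57, 4.80. Sum of squares 44.0; √(44.0/2) = 4.7.

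The month-3 data have to be in the model.

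**5. If month 3 is added, quadratic or categorical visit?** A four-visit quadratic fits 6 parameters to 8 cell means, so it can bend visit-specific differences. The documents give no expected trajectory, so these are illustrations. Entries are the between-arm change at completion / 1 month / 3 months.

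| Assumed truth | Fitted, T = 42 | T = 60 | T = 70 |
|---|---|---|---|
| 1 / 1 / 1 | 0.81 / 1.09 / 0.93 | 0.88 / 1.08 / 0.96 | 0.91 / 1.07 / 0.97 |
| 1 / 0.75 / 0.50 | 0.71 / 0.88 / 0.40 | 0.80 / 0.88 / 0.43 | 0.83 / 0.88 / 0.44 |
| 0.50 / 0.75 / 1.00 | 0.50 / 0.75 / 1.00 | 0.53 / 0.73 / 1.01 | 0.54 / 0.72 / 1.01 |

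Against that quadratic, categorical visits raise the SE of the between-arm change by 34% (T = 42) to 21% (T = 70) at completion, 5% to 10% at one month, and 3% to 2% at three months. Example at T = 42: the categorical SE at completion is √(2(1 − 0.6) × 2/24) = 0.26 SD, against 0.26/1.34 = 0.19 SD for the quadratic.

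**The case against.** The strongest reply is that AM-PAC does have a stated model. The three-occasion clause explains why a repeated-measures model is used and does not restrict the data, and a mixed model takes a fourth visit without change. It is true that month 3 is not expressly excluded and that the model family is given. But the sentence lists the occasions and leaves month 3 out, and no month-3 contrast appears anywhere, so the gap in pre-specification stands.

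On OASIS, the rank failure depends on visit-time coding, which the plan does not state, and the useful contrast survives under either coding. Both points are correct. The quadratic still serves no purpose there, and its curvature is either unidentified or driven by length of care.

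The primary outcome is untouched at its measured visits and this is a 48-patient pilot aimed at estimation. That limits the weight of the point. Nobody proposes extrapolating to month 3; those figures only show that a three-visit fit is no substitute. The preference for categorical visits does rest on a trade-off, since one illustrated trajectory shows almost no distortion and precision at completion is lost. A quadratic over all four visits is therefore a legitimate option.

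OASIS scores are extracted at discharge or 60 days after admission, so some patients may have no discharge score by then. That is a separate matter which the fix here does not resolve.

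**Conclusion.** The concern holds and should be fixed. One of the three occasions in the primary objective has no stated analysis, and AM-PAC is the only ADL measure that can supply it. The OASIS quadratic is not identified on visit time (rank 4 of 6, or 4 of 5 with shared curvature). On actual dates it would rest only on between-patient differences in timing.

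The visit counts come straight from the documents. The ranks need only the assumed arm-by-time terms. The SE ratios also rest on complete data, compound symmetry and the assumed completion day; the OASIS date figures rest on assumed interval distributions.

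AMPS and the physical tests at their measured visits are not affected, provided each arm has its own linear and quadratic terms. The OASIS between-arm difference in change remains estimable.

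**What to change.** 1. Replace the general three-occasion statement with time points listed by outcome.
2. For AM-PAC, include all four visits and pre-specify the between-arm difference with 95% CI at completion, one month and three months. Categorical visit with arm-by-visit terms is preferred. An arm-specific quadratic over all four visits is acceptable if its shape assumption is stated.
3. For AMPS and the physical tests, state arm-specific linear and quadratic terms or, equivalently at three visits, arm-by-visit terms. State how time is coded.
4. For OASIS, drop the quadratic and use a two-time-point analysis: the difference in change, or the discharge score adjusted for the start-of-care score.
5. Restate the hypothesis by outcome: AMPS to one month, AM-PAC to three months, OASIS at discharge.

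The cost is a few sentences and slightly different model code, with no new data or patients. The 3-month claim narrows to AM-PAC. Categorical visits use 8 mean parameters instead of 6, and lose precision against a four-visit quadratic mainly at completion.
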